9.3.2.5 Treatment Volume

[figure not shown]
[REDACTED]

The total volume injected in each upper quadrant will be collected for each study device. Additionally, total volume required injected in each lower quadrant will be collected. Treatment volume will be measured to an accuracy of 0.1 mL.

9.4 Safety

Safety will be evaluated through a 30-day patient Common Treatment Response (CTR) diary that captures post-injection signs/symptoms and AE reporting based on phone follow-ups and clinic visits.

9.4.1 30-Day Patient Common Treatment Response Diary

The subject will receive a diary booklet and instructions for recording his/her observations of the CTRs of the study treatments for the first 30 days after treatment. The diary will be dispensed after treatment and will be discussed during the 72-hour post-injection telephone follow-up. Subjects should complete the diary at approximately the same time each day (i.e., AM or PM).

The subject diary will capture the following CTRs that typically occur following the injection of a dermal filler; specifically, redness, pain, tenderness, firmness, swelling, lumps/bumps, bruising, itching, discoloration, and “other”. Subjects will record the presence and the severity of each observed sign/symptom as: none, mild, moderate, or severe.

The 30-day patient CTR diary will capture the daily occurrence of each CTR. The 30-day patient CTR diary will include a detailed glossary describing all signs/symptoms listed in the diary.

9.4.2 72-Hour Telephone Follow-up

The subject will be contacted by telephone by the investigational site approximately 72 hours following study injections and will be queried regarding health status and AEs. Information gathered will be documented in the progress notes and upon confirmation at the next clinic visit, data will be entered into the eCRF. The investigational site must attempt at least twice to contact

the subject. All failed attempts will also be documented in the study notes.

[Redacted text block containing multiple paragraphs of obscured content]

9.4.5 Pregnancy and Contraception

A female of childbearing potential must present a negative UPT prior to injection of the study device. Subjects who are pregnant are excluded from the study.

Female subjects of childbearing potential are expected to prevent pregnancy occurring whilst on treatment by using effective birth control methods (e.g., oral contraceptive, condom, IUD, injectable contraceptive, diaphragm or vasectomized partner). Male subjects have no contraceptive restrictions.

9.4.6 Adverse Events

All observed or volunteered AEs regardless of treatment group or suspected causal relationship to

the study device(s) will be recorded in the eCRF. Subjects will be questioned for the occurrence of any new or worsening signs or symptoms at each visit by the following methods:

- Information volunteered by the subject
- Open ended and non-leading questions such as: Have you had any health problems since your last visit?
- Observation by the investigational team, other care providers or relatives

9.4.6.1 Definition of an Adverse Event

An AE is any untoward medical occurrence in a subject administered the study device and which may, but does not necessarily, have a causal relationship with the device. An AE can therefore be any unfavorable or unintended sign (for example an abnormal laboratory finding), symptom or disease temporally associated with the use the study device, whether or not considered related to that device.

AEs may include, but are not limited to, subjective or objective symptoms spontaneously offered by the subject, solicited via the diary and subject interviews, uncovered by review of concomitant medications or therapies, and/or observed by the study site staff. The TI will determine the description (sign, symptom, or diagnosis), onset, resolution, seriousness, severity, cause and action taken for any event.

CTRs will not be considered AEs unless the duration and/or severity exceed what is typically observed following injection of a dermal filler, and are clinically significant as determined by the TI. CTRs will be reviewed by TI to ensure that CTRs are elevated to the status of an AE as appropriate, and will determine AE severity and the relationship to the study devices. CTRs that are present on day 30 of the diary (or on the last recorded day of the diary) will by default be elevated to the status of an AE, regardless of TI assessment.

Disease signs and symptoms that existed prior to the study injections are not considered AEs. Recurring symptoms associated with pre-existing conditions are not considered AEs unless they have a clinically significant increase in severity and/or frequency, as determined by the TI.

Clinically significant abnormal laboratory tests (if applicable) must be recorded as an AE.

Changes resulting from normal growth and/or development occurring at a physiologically appropriate time that do not vary significantly from the frequency or severity expected, for example, the onset of menses or menopause, are not to be considered AEs.

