8.2 Subject Diaries

Subjects will record Common Treatment Responses (CTRs) for 30 days post-injection using paper-based diaries. Data recorded in this diary will be entered into the eCRF by the study coordinator.

Subjects will also record “duration of anesthetic effect” using paper-based diaries. Data recorded in this diary will be entered into the eCRF by the study coordinator.

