9.2.3 Visit 2 (30 days from V1; ±3 days)

- Concomitant medications/treatments
- Photography

- TI Assessments

[Redacted]

[Redacted]

- Subject Assessments

[Redacted]

- Collect and review CTR Diary and “Duration of Anesthetic Effect” Diary

- Next Study Visit

- *If Subject presents with an unresolved device related clinically significant AE, proceed to Follow-up Phone Call.*
- *If Subject does not present with an unresolved device related clinically significant AE, the subject will **exit** the study and optional treatment with a commercially available product approved for injection into the perioral rhytids will be offered to subjects with remaining lines and/or wrinkles in the no-treatment zone.*

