11.8 Safety Analysis

The SAFT Population will be used to summarize the safety of the study devices and will consist of all treated subjects. The primary safety analysis is the calculation of the incidence of CTRs and adverse events in the study period. Point estimates for all CTRs, AEs and SAEs will be presented and two-sided exact 95% confidence intervals will be calculated for the overall incidence of AEs and SAEs. Tables will be generated which summarize AEs by investigator assessments of both relationship to treatment and severity.

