11.8.1 Adverse Events (AEs)

Safety outcomes will be incidence rate of AEs, including UADEs, types of AEs and their relationship to study treatment. Severity and relationship to study treatment will be assessed and recorded.

AEs will be coded using the Medical Dictionary for Regulatory Activities (MedDRA) dictionary. These events, irrespective of relationship to study medication, will be summarized by MedDRA system organ class (SOC) and MedDRA preferred term (PT). The number of subjects reporting an AE, the number of AEs, and percentages of subjects in each category will be summarized. AEs by severity and relationship to study will be summarized in a similar way. Serious AEs will be summarized separately. Specifically, the following AE incidence tables will be provided:

- All and possibly* related AEs sorted by SOC
- All and possibly* related AEs sorted by decreasing frequency
- SAEs: All and possibly* related SAEs sorted by seriousness criterion
- SAEs: All and possibly* related SAEs sorted by SOC
- UADEs: All and possibly* related UADEs sorted by SOC
- Death: All and possibly* related deaths sorted by SOC

* *definitely probably, possibly*

Incidence rates with two-sided exact 95% confidence intervals will be calculated for the overall incidence of AEs and SAEs

Statistical analysis will also be performed to evaluate the potential impact of the injection technique on the safety data.

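### Does the last-diary-day rule for common treatment responses make adverse event incidence depend on when Visit 2 happens?

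*Protocol*

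**What the plan says.** Protocol section 8.2 sets the diary length: "Subjects will record Common Treatment Responses (CTRs) for 30 days post-injection using paper-based diaries". Section 9.4.1 adds that "The 30-day patient CTR diary will capture the daily occurrence of each CTR". Section 9.2.3 places Visit 2 at 30 days from Visit 1 with a window of three days either side. One of its tasks is to "Collect and review CTR Diary and" the diary on duration of anesthetic effect. Under the same section, a subject with no unresolved clinically significant device-related AE leaves the study at that visit.

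Section 9.4.6.1 has two routes from CTR to AE. The ordinary route needs duration or severity beyond the typical, and clinical significance in the treating investigator's judgement. The default route needs no judgement: "CTRs that are present on day 30 of the diary (or on the last recorded day of the diary) will by default be elevated" to AE status.

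Incidence of CTRs and AEs is the primary safety analysis (Protocol 11.8, SAP 6.8), and "two-sided exact 95% confidence intervals will be calculated for the overall incidence of AEs and SAEs". The visible tables sort AEs by system organ class, frequency and seriousness, and "AEs by severity and relationship to study will be summarized in a similar way". None separates AEs that arise only by default. Much of the text around the diary description and the SAP's tabulations is blacked out, so a rule on incomplete diaries may exist there.

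**The concern.** Read together, these sections let an administrative date decide a safety classification. Take a mild CTR that clears on day 29. If Visit 2 falls on day 27 and the diary is handed in then, the CTR is present on the last recorded day and becomes an AE automatically. If the diary runs to day 30, the same CTR is an AE only if the investigator judges it so. Neither subject has deviated from the protocol. A diary abandoned early with a CTR still marked is caught in the same way.

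With at most 30 subjects, each extra subject with an AE moves overall incidence by up to 3.3 percentage points. A reader of the visible tables could not tell a default AE from one the investigator thought clinically significant. What would be at stake is the absolute AE rate reported for the two fillers.

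**Working it through.** The plan gives no figure to reproduce: no AE rate, CTR duration, visit-date spread or rate of early diary stopping is visible. The check therefore has two parts.

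**Reading the rules together.** The window runs from day 30 − 3 = 27 to day 30 + 3 = 33. A compliant diary can end up to three days short of day 30; visits on days 30 to 33 allow a full diary. If treatment day counts as diary day 1, which is not visible, the loss is at most two days. So AE status can depend on the diary's end day.

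**Size, under stated assumptions.** Suppose each subject has one CTR from day 0. Let the probability that it is still present on day t be S(t) = 2^(−(t/m)^k), with median duration m from 7 to 14 days and Weibull shape k from 0.7 to 1.5 (k = 1 is exponential). These inputs are assumptions.

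- *All 30 diaries end on day 27.* Extra subjects with a default AE = 30 × [S(27) − S(30)]. Minimum, at m = 7 and k = 1.5: 30 × (0.0052 − 0.0021) = 0.09. Maximum, at m = 14 and k = 1.465: 30 × (0.1630 − 0.1204) = 1.28. With k = 1 the range is 0.53 to 1.09.
- *Visits spread evenly over days 27 to 33, later ones with full diaries.* Extra = (30/7) × the sum over d = 27, 28, 29 of [S(d) − S(30)]. Range: 0.02 to 0.35.
- *Three independent CTRs per subject.* Replace S(t) by 1 − [1 − S(t)]³. All diaries ending on day 27: 0.28 to 2.87. Spread visits: 0.07 to 0.80.
- *One diary stopped on day 7, independently of symptoms, one CTR.* Extra = S(7) − S(30). Range: 0.35 (m = 14, k = 0.7: 0.6527 − 0.3067) to 0.67 (m = 12.9, k = 1.5: 0.7578 − 0.0853) of a subject.

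Two features push these figures in opposite directions. Some of these CTRs would become AEs on the investigator's judgement anyway, which lowers the effect. The diary lists nine named responses plus a category for others, so a subject may have several, which raises it. None of the ranges is therefore an upper bound.

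**Against the precision of the estimate.** One subject is 1/30 = 3.3 points. As an illustration, 3/30 = 10.0% has an exact 95% interval of 2.1% to 26.5%, and 4/30 = 13.3% has 3.8% to 30.7%. A shift of one whole subject is small beside intervals about 24 to 27 points wide.

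**The case for a change.** The best case for a change is that conservatism does not remove the dependence on diary length, and that making it visible looks cheap. Subjects seen on days 27 to 29 could finish the diary and send it back, default AEs could be flagged, and incidence could be shown with and without those from short diaries.

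The first part stands: the dependence is there, and the visible tables do not show it. The remedies do less well.

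- *Completing the diary later.* Under section 9.2.3 most subjects leave the study at Visit 2, so entries for days 28 to 30 would fall after exit. Section 9.4.6.1 also has the investigator review the CTRs, so a late diary would need a second review. That means reworking the exit and collection steps, which is more than a sentence.
- *Reporting incidence without default AEs from short diaries.* This treats every one of those CTRs as resolved by day 30. Some would not be, so the row errs downward, in the less cautious direction for a safety count.
- *Flagging alone.* This is harmless but changes no conclusion. The inputs for a descriptive listing largely exist: section 8.2 says of the CTR diary that "Data recorded in this diary will be entered into the eCRF by the study coordinator", and section 9.4.6.1 has onset and resolution determined for each event.

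A diary that stops very early can matter more for that one subject than the visit window does. No stopping rate is given, so no trial-level size can be attached to it. Counting a CTR last seen as present is also the cautious reading when nothing later was recorded.

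**Conclusion.** No change to the plan is needed. The words about the last recorded day show that the sponsor foresaw diaries ending before day 30 and chose to count an unresolved CTR as an AE. Section 9.4.9 takes the same line, asking for an event to be reported where its AE status is in doubt. Following the plan as written gives a sound, conservative AE count.

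The effect is confined to absolute AE incidence. CTR incidence is reported in its own right, and the primary pain endpoint is assessed on the day of injection. Because the design is split-face with one Visit 2 date per subject, the rule is unlikely to favour either device.

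If visits spread over the window, the expected excess is probably below one subject in 30: 0.02 to 0.35 with one CTR per subject and 0.07 to 0.80 with three. This rests on assumed median durations of 7 to 14 days and Weibull shapes of 0.7 to 1.5. It would be larger if nearly all subjects attended on the first permitted day or if many CTRs per subject ran close to day 30. Analysts who want the detail can list default AEs with the last diary day, as description only, from data already held.

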9.4.8 Serious Adverse Events (SAEs) and Unexpected Adverse Device Effects (UADEs)

A **SAE** is defined as any unfavorable medical occurrence that meets any of the following:

1. Results in death.
2. Is life-threatening: “Life-threatening” refers to an event in which the subject was at risk of death at the time of the event; it does not refer to an event, which hypothetically might have caused death if it were more severe.
3. Requires inpatient hospitalization or prolongation of existing hospitalization: Planned and routine hospital admissions for pre-existing conditions are not considered SAEs and do not require reporting as an AE unless the condition has worsened beyond what would reasonably be expected for that subject. If a subject experiences an additional AE that prolongs a pre-planned hospitalization this is considered to be an SAE and should be reported as an SAE. Pre-planned admissions must be recorded in the subject’s source documentation.
4. Results in persistent or significant disability/incapacity.
5. Is a congenital anomaly or birth defect resulting from a pregnancy that occurred during the study.
6. Is an important medical event: Important medical events that may not be immediately life-threatening or result in death or hospitalization but may jeopardize the subject or may require intervention to prevent one of the other outcomes listed above should usually be considered serious.

A **UADE** is defined as any device-related AE that meets any of the following:

1. Is not identified in nature, severity or frequency in current literature on the product.
2. Is life threatening, even if temporary in nature.
3. Results in permanent impairment of a body function or permanent damage to a body structure.
4. Necessitates medical or surgical intervention to preclude permanent impairment of a body function or permanent damage to a body structure.
5. Any device malfunction that would be likely to cause or contribute to a death or serious injury if the malfunction were to recur.

9.4.9 Causality Assessment

The TI’s assessment of an AE’s relationship to the study device is part of the documentation process, but it is not a factor in determining what is or is not reported in the study. If there is any doubt as to whether a clinical observation is an AE, the event will be reported. The TI will assign the causality assessment according to his/her clinical experience and the subject’s description of the event. The Sponsor will be responsible for the final causality judgment. The causal relationship should be classified according to the following criteria (not all variables need to be present to be indicative of relationship to the device):

Definitely related:

- The temporal sequence of AE onset relative to injection of study device is reasonable.
- The AE is more likely explained by the study device or procedure than by another cause.
- The AE shows a pattern consistent with previous knowledge of the study device.

Probably related:

- The temporal sequence of AE onset relative to injection of study device is reasonable.

- The AE is more likely explained by the study device or procedure than by another cause.

Possibly related:

- The temporal sequence of AE onset relative to injection of study device is reasonable.
- The AE could have been due to another equally likely cause.

Probably not related:

- There is another more likely cause of the AE.

Definitely not related:

- The temporal sequence of AE onset relative to injection of study device is not reasonable.
- There is another obvious cause of the AE.

9.4.10 Severity Assessment

For events reported on the AE eCRF, the TI will determine the severity classification based on his/her clinical experience and by using the following definitions of severity (note: a “severe” AE is not the same as a SAE):

- Mild: Symptoms are barely noticeable or do not make the subject uncomfortable. The AE does not influence performance or functioning. Prescription drugs are not ordinarily needed for relief of symptom(s).
- Moderate: Symptoms are of sufficient severity to make the subject uncomfortable. Performance of daily activities is influenced. Treatment of symptom(s) with prescription drugs or therapies may be needed.
- Severe: Symptoms are of sufficient severity to cause the subject severe discomfort. Performance of daily activities is compromised. Treatment for symptom(s) with prescription drugs or therapies may be needed.

The maximal severity for the AE will be recorded, even if the AE presented as being less severe at some point during the event.

9.4.11 Adverse Event Reporting

9.4.11.1 All Adverse Events

All AEs, whether serious or not, will be recorded from the time of informed consent until the last study visit, or until 30 days following the study treatment. The TI will assess all AEs and record details of seriousness, severity, duration, and action taken with study device, and relationship to the study device.

If an AE occurs, the first concern will be the safety of the study participants. All Device Related AEs occurring after study device administration will be followed until the event has resolved or stabilized or until follow-up is no longer possible or the TI deems it unnecessary.

The Sponsor is responsible for reporting AEs to the relevant governing authorities in the time frame applicable according to international and local law.

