9.2.4 Follow-up Phone Call – Optional (no later than 30 days from V2)

- Concomitant medications/treatments review

- AE review

- *Confirm if subject is still experiencing the unresolved clinically significant device related AE(s)*
 - *If yes, the site will request that the subject attend the optional in-clinic within 5 working days.*
 - *If no, the subject will **exit** the study*

[Redacted]

[Redacted]

[Redacted]

[Redacted]

[Redacted]

[Redacted]

[Redacted]

[Redacted]

[Redacted]

[Redacted]

[Redacted]

[Redacted]

- Study Exit

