9.4.11.2 Serious Adverse Events (SAEs) and Unexpected Adverse Device Effects (UADEs)

All SAEs and UADEs that occur after the time of informed consent through 7 days after subject completion of the study, or within 30 days following the study treatment, must be reported to [REDACTED]. Initial reports must be made by contacting [REDACTED] as per the following: Contact the [REDACTED] by telephone and **complete the**

[REDACTED]

SAE/UADE Form and submit by [REDACTED] or by email. [REDACTED]

[REDACTED] It is the site's responsibility to perform the following:

- Obtain and maintain all pertinent medical records, information, and medical judgments from colleagues who assisted in the treatment and follow-up of the subject.
- Provide [REDACTED] with a complete, written case history, including copies of supporting reports (e.g., progress notes, laboratory reports) and a statement as to whether the event was or was not related to the use of the study device.
- With the assistance of [REDACTED], notify the governing IRB of the SAE or UADE in accordance with the requirements of SAE reporting stipulated by the governing IRB.

Reporting Timelines

UADEs: The site must report UADEs [REDACTED] within 24 hours of awareness of the event. Within 24 hours of receiving the UADE report from the site, [REDACTED] must report the UADE to the Sponsor. As per 21 CFR 812.46 (US), the Sponsor must investigate the UADE and report the results to the FDA and IRB within 10 working days of receiving the report from [REDACTED].

- **SAEs:** The site must report the SAE to the [REDACTED] within 24 hours of becoming aware of the event. Within 24 hours of receiving the SAE report from the site, [REDACTED] must report the SAE to the Sponsor. Sponsor must investigate the SAE and, if it is device related, will report the results to the FDA and IRB within 10 working days of receiving the report from [REDACTED].

Study Hold Due to UADEs

- If the Medical Monitor determines that an UADE(s) presents an unreasonable risk to subjects, the Sponsor shall put on hold all investigation or parts of investigations presenting that risk as soon as possible. The study hold shall occur no later than 5 working days after the Sponsor makes this determination and not later than 15 working days after the Sponsor first received notice of the effect. The Sponsor will not resume an on hold investigation without IRB and FDA approval.

[REDACTED]

[REDACTED]

[REDACTED]

[REDACTED]

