10 SUBJECT COMPLETION / WITHDRAWAL / STOPPING RULES

10.1 Completion

A subject will be considered to have completed the study if he or she has completed all the assessments or has experienced an event that precludes further participation in the study.

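### Do the two alternative end dates for AE recording, and the later one for SAE reporting, leave the safety analysis window open?

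*Protocol*

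**What the plan says.** Protocol 9.4.11.1 has adverse events "recorded from the time of informed consent until the last study visit, or until 30 days following the study treatment". The sentence opens with "All AEs, whether serious or not", so it covers serious events too. Protocol 9.4.11.2 requires SAEs and UADEs to be reported when they occur "through 7 days after subject completion of the study, or within 30 days following the study treatment". Neither sentence says whether the earlier or the later end applies.

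The calendar comes from 9.2.3, headed "Visit 2 (30 days from V1; ±3 days", that is, days 27 to 33. "If Subject does not present with an unresolved device related clinically significant AE", the subject leaves the study at that visit. Otherwise an optional call follows under 9.2.4, "Optional (no later than 30 days from V2", and possibly Visit 3. Section 10.1 sets the anchor for the 7-day tail: "A subject will be considered to have completed the study if he or she has completed all the assessments", or has had an event that rules out further participation.

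Protocol 9.4.6 has all AEs that are observed or volunteered entered in the eCRF, and subjects asked about new or worsening symptoms at every visit. Protocol 11.8 and SAP 6.8 make AE incidence over the *study period* part of the primary safety analysis, with exact 95% intervals for overall AE and SAE incidence. The readable text does not define that period. Large parts of Protocol section 11 and of the SAP around and after 6.4.3 are blacked out and may do so.

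**The concern.** Read literally, the recording sentence gives two stopping points and the reporting sentence a third. A subject who exits on day 27 has candidate ends at days 27, 30 and 34; one who exits on day 33 has days 33, 30 and 40. An SAE on day 36 in a subject who left on day 30 falls within the 7-day reporting tail but after both ends of the AE sentence, although that sentence expressly includes serious events.

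The primary safety result is an incidence in at most 30 subjects, where each subject counts for 3.3 percentage points. If the window is not fixed beforehand, whether a late event enters the table could be decided after it is known. The SAP says its purpose is to prevent this kind of choice, yet SAP 6.8 repeats the protocol's phrase without defining it.

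**Working it through.** **Inputs.** Day 0 is Visit 1, when treatment is given. Visit 2 falls on day *v*, from 27 to 33 (Protocol 9.2.3). The optional call comes at most 30 days later (9.2.4). At most 30 subjects are treated (4.2.1).

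**The plan's own figure.** The synopsis gives a study duration of about 60 days. Visit 2 at day 30 plus a call up to 30 days later gives 30 + 30 = 60, so the calendar is read correctly.

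**End dates for a subject who exits at Visit 2.** Last visit = *v*; 30-day rule = 30; reporting tail = *v* + 7.

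| Exit day | Last visit | 30-day rule | Later of the two | Completion + 7 | Days from later end to tail end |
|---|---|---|---|---|---|
| 27 | 27 | 30 | 30 | 34 | 4 |
| 28 | 28 | 30 | 30 | 35 | 5 |
| 29 | 29 | 30 | 30 | 36 | 6 |
| 30 | 30 | 30 | 30 | 37 | 7 |
| 31 | 31 | 30 | 31 | 38 | 7 |
| 32 | 32 | 30 | 32 | 39 | 7 |
| 33 | 33 | 30 | 33 | 40 | 7 |

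**Which readings survive.** An earlier-of-the-two rule would discard a new event that a subject reports at a day-33 Visit 2, or at Visit 3. Protocol 9.4.6 requires that event to be asked about and recorded, so the earlier-of reading fails. What remains is a choice between the last visit and the later of the two ends. These agree for every exit on day 30 or after. They differ by 3, 2 and 1 days for exits on days 27, 28 and 29.

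**Size of the AE gap.** Assume that all 30 subjects exit at Visit 2 and that visit dates spread evenly over the seven days.

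- Mean gap per subject: (3 + 2 + 1)/7 = 0.857 days.
- Over 30 subjects: 30 × 0.857 = 25.7 subject-days.
- Total to the last visit: 30 × 30 = 900. Total to the later end: 900 + 25.7 = 925.7.
- Share: 25.7/925.7 = 2.8%.

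The documents give no AE rate. At an assumed constant 0.1 to 0.5 new AEs per subject per 30 days, the gap holds (25.7/30) × 0.1 = 0.09 to (25.7/30) × 0.5 = 0.43 events across the whole study.

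**The SAE sentence.** Section 9.4.11.2 says which events must be reported. An event that meets either of its two conditions is reportable, so its *or* is inclusive and needs no selector. It is also a duty to notify by telephone and form within 24 hours, which is a different function from the recording rule in 9.4.11.1. A longer tail for notifying serious events does not in itself contradict a shorter recording window.

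**Tabulating an SAE in the tail.** The SAE tables listed in Protocol 11.8.1 and SAP 6.8.1 cover all SAEs and state no cut-off date. With exact (Clopper-Pearson) limits:

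- 0/30: upper limit 1 − 0.025^(1/30) = 11.6%, so 0% (0 to 11.6%).
- 1/30: 3.3% (0.1 to 17.2%).

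This shift needs an SAE to occur 4 to 7 days or less after the later AE end, and then to be left out of the table. No readable text provides for leaving it out.

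**The case for a change.** The strongest case is that the operative sentences are readable and still name no governing end. The AE sentence expressly covers serious events, so separating recording from reporting does not fully settle the SAE tail. On the later-of reading, a subject who exits on day 27 needs AE information up to day 30, and no readable step schedules a contact after exit. The rule that device-related AEs are followed until resolved concerns events already recorded, not new ones. Under 10.1 a subject can also complete early: completion on day 10, for illustration, gives 10 + 7 = 17 by the tail against day 30 by the other condition. A sentence or two would settle all of this before the data are seen.

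Part of it stands. The wording is loose, and the readable text does not say whether an SAE notified after exit is counted or only listed. The early-completion example does not make SAE reporting ambiguous, because under the inclusive reading the 30-day condition still applies. For AE recording the two ends would lie further apart in such a subject than in the table, but Protocol 10.2 asks withdrawn subjects to attend their next scheduled visit and to allow continued safety monitoring, which fits the later-of reading. The missing contact on days 28 to 30 is a limit on collection, and wording alone would not remove it. Adding a contact would be extra work for at most three days of follow-up.

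**Conclusion.** No change to the plan is needed. This is a gap in detail that analysts would fill sensibly: record to the later of the two ends, and tabulate every SAE that is reported. The window is not unset. Given 9.4.6, the AE ends differ only on days 28 to 30, for subjects who exit on days 27 to 29. That is 2.8% of follow-up if all subjects exit at Visit 2 and visits spread evenly, and less than half an event at the assumed AE rates. The SAE question matters only if an event falls in a tail of 4 to 7 days among at most 30 subjects; the most that one such event does is move the estimate from 0% to 3.3%.

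Both devices are injected in the same subject and share that subject's window, so no effect is shown on the within-subject comparison. The primary endpoint is rated at Visit 1 and is untouched. No reading of the dates has been shown to alter the safety conclusion. Asking the sponsor to state which end applies would tidy the text without offering a better rule than the natural one, and a definition of the analysis period may already stand in the blacked-out text.
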